6.5 Monitoring for Subject Compliance

Subject compliance will be based on three assessments, namely, the level of completion of patient 7-day voiding diary, attendance at scheduled follow-up visits plus evaluation of the internal memory of the Neurotech Vital Compact device and the itouch Sure Pelvic Floor Exerciser or the Device Record (diary) to check daily use parameters and schedules.

7 Study Treatments

One device will be issued to each randomized subject in a single-blinded manner. The investigator and those administering the 1-hour provocative stress test, evaluating adverse events and reviewing diary data are to remain blinded regarding treatment assignment.

7.1 Description

The Neurotech Vital Compact Device consists of a controller and a garment.

7.1.1 Neurotech Vital Compact Controller

The Neurotech Vital Compact Controller is a powered Neuromuscular Electrical Stimulation (NMES) device manufactured by Bio-Medical Research Ltd.

The Neurotech Vital Compact Controller is manufactured as a sealed, handheld portable unit containing electronics and a rechargeable battery with an LCD screen and keypad for interaction with the user (see Figure 1). The outer casing is manufactured from ABS resin and the device has been independently certified to comply with IEC60601-1-1 and IEC60601-2-10.

The Neurotech Vital Compact Controller is CE Mark approved as a Class IIa Device in Europe, in line with Medical Device Directive 93/42/EC as last amended by 2007/47/EC, and will be used in accordance with the Instructions for Use.

Figure 1. The Neurotech Vital™ Compact device Controller

The stimulation current is delivered to the body through an array of conductive adhesive electrodes (in accordance with the pre-defined parameters) which are held in place by a garment which wraps around the buttocks and thigh area (see Table 1). This ensures the current passes from the electrode set on one side of the body to the other and this approach has been found to be particularly effective in activating the pelvic floor muscles.

Table 1. Parameter Specifications on the Neurotech Vital Compact Controller

Duration of each session	Frequency	Pulse Width	Ramp-Up time	Contract Time	Ramp Down Time	Relax time	The pulse is a conventional
30 minutes	50Hz	620µs	0.5 seconds	5 seconds	0.5 seconds	5 seconds	

1 symmetric biphasic type with constant current control. The phase duration is 620µs and the maximum current amplitude is 120mA, leading to a maximum charge per pulse of 74 µC. The maximum rms current of this pattern is 30mA. The total power from the device at maximum output intensity setting with all electrodes active into a 500Ω load is 0.45 W. This maximum is comparable to the available power from several 8-electrode systems which are already cleared to market by the US Food and Drug Administration (FDA). For example Compex Sport (K011880) delivers up to 0.48W (100mA @ 120Hz, phase duration=400 µs).

Subjects will be at liberty to alter the intensity of the stimulation to the highest tolerable level and provided with guidance on the intensity of the muscle contraction to be achieved.

The Neurotech Vital Compact Controller will only permit stimulation if the garment is connected to the unit.

For purposes of this study, the Neurotech Vital Compact is to be used per the Instructions for Use (IFU) provided in Appendix XI. A Vital Compact Quick Start Guide is also included in Appendix XI.

7.1.2 Neurotech Vital Garment

The Neurotech Vital Compact Garment is intended for use with the Neurotech Vital Compact Controller to aid the placement of the electrodes and to help keep them securely in place (see Figure 2). The garment is made from an outer material which is 80% nylon, 20% elastane and a100% polyurethane inner. Fasteners are manufactured in nylon. All of these materials have been extensively used and documented for their biocompatibility with human skin. The garment will be used in accordance with the Instructions for Use.

Figure 2. The Neurotech Vital Compact device connected to the garment

7.1.3 Hydrogel Electrodes

The hydrogel electrodes are comprised of a three-layer conductive medium to deliver the electrical current. The electrodes are manufactured by Axelgaard (Fallbrook, C.A USA), a leading supplier to the medical device sector, and have undergone rigorous safety and biocompatibility testing. The double adhesive electrodes in the Neurotech Vital Compact device measure 15.0 by 10.5 cm and disperse the current over a large area of skin resulting in a low current density. The maximum current density remains low at less than 0.05 mA/cm^2 which is typical of TENS devices used in clinical practice.

The hydrogel electrodes are CE Mark approved as a Class I Device in Europe, in line with Medical Device Directive 93/42/EC as last amended by 2007/47/EC.

7.1.4 Pre-clinical Data

The Neurotech Vital Compact Controller has been tested by an independent test house (SGS, UK) and certified to be in conformance with the requirements of the IEC60601 series of standards. The controller is CE-marked under the European Medical Device Directive, authorised by the notified body, VDE Germany. The garment and electrode materials are certified to be in conformance with bio-compatibility standard ISO 14993.

There are no tissues of human or animal origin or any medicinal substances used in the garments, electrodes, or Neurotech Vital Compact device.

7.2 itouch Sure Pelvic Floor Exerciser

The itouch Sure Pelvic Floor Exerciser is manufactured by TensCare Ltd., [name].

This is an intravaginal device that will be used daily for 20 minutes. Further details on the itouch Sure Pelvic Floor Exerciser are presented in the 510(k) Summary (see Appendix II) and Instructions for Use (Appendix XII). The device will be used in accordance with the Instructions for Use provided for this study for treatment of stress incontinence.

7.2.1 Packaging and Labelling

The Neurotech Vital Compact device will be provided packaged, along with its electrode lead and hydrogel electrodes, in a box with an identifying serial number, part number and subject number. The device will also bear the CE mark.

The Neurotech Vital garments will be separately packaged and also will have their own identifiable lot numbers. Expiry dates will also be found on the electrode packaging.

The itouch Sure Pelvic Floor Exerciser will be provided packaged, along with vaginal lubricating gel, in a box with identifying serial number and subject number. The device will bear the CE mark.

Each device will be in packaging with a label with at least the following information:

For Clinical Trial Use Only

Study Number: BMR-13-1001

Contents: One Neurotech Vital Compact or itouch Sure Pelvic Floor Exerciser

Subject Number: XXXXX

Treatment Duration: 12 weeks at 30 minutes 5 days a week (Neurotech Vital Compact) or 12 weeks of 20 minutes 7 days a week (itouch Sure Pelvic Floor Exerciser)

Lot number: XXXXXXXX

Storage: Store at ambient (room) temperature

Study Sponsor and Manufacturer for Neurotech Vital Compact: Bio-Medical Research Ltd., [name].

US Study Director Expedite Research, LLC, [name]

Caution: The Neurotech Vital Compact is an investigational device limited by US Federal Law to be used by qualified Investigators only.

7.3 Device Storage and Accountability

Formal accountability will be performed for all devices. The Investigator will be provided with a Device Accountability Log to track disposition of all devices including the itouch Sure Pelvic Floor Exerciser, Neurotech Vital Compact devices, hydrogel electrodes and Neurotech Vital garments (left and right).

All devices must be stored in a secure place at ambient temperature. It is the responsibility of the Investigator to ensure that devices are stored correctly at the site. The Investigator must also make the devices, eCRFs, clinic notes and Investigator File available for inspection by the monitor upon request.

During this clinical study or upon its completion or termination, the Investigator will return all devices to Bio-Medical Research Ltd. Bio-Medical Research Ltd will keep a record of the number of devices provided and returned.

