8.5 Study Recruitment

Subjects who attend the clinic for treatment of urinary stress incontinence will be approached by the Investigator to take part in the clinical study. Additionally, an approved advertisement will be made available to sites if they wish to advertise to recruit subjects into this clinical study.

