8.7 Subject Eligibility

Once written informed consent has been obtained, the Case Report Form will be completed to document adherence to the inclusion and exclusion criteria.

Where a subject fails to fulfill any element of the inclusion and exclusion criteria, this will be documented and the signed consent form and completed inclusion/exclusion criteria retained by the Investigator. The subject will not be advanced further in the study.

When a subject is considered eligible for entry into the study, the subject will be randomized to the next available subject number (subject ID number). This number will be the unique identifier of the subject and written on each page of the Case Report Form and all other study documentation relating to the subject.

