8.8 Randomisation

At the initiation visit, the designated personnel will be trained regarding how to conduct and document the randomisation of subjects enrolled into the study at that site.

The site will be provided with randomisation envelopes which will be used to allocate the devices. Access to these randomisation envelopes will be limited to the designated un-blinded personnel working on the study at the site.

When a subject has agreed to participate in the study, given informed consent, and is considered eligible with the inclusion/exclusion criteria, she will be entered into the study and only then will she be randomised to either device. The designated un-blinded personnel will train the subject according to which treatment has been allocated.

In the event of an emergency whereby it becomes necessary to know to which treatment the subject has been allocated, the investigator may be made aware of the allocated treatment via the unblinded personnel at the site. A documented procedure will be provided to the site before the study commences.

All baseline assessments must be completed prior to randomisation.

8.9 Screening Assessments – Visit 1

Each subject considered eligible for entry into this clinical study, and from whom written consent has been obtained, will have a screening assessment with the following information/procedures recorded (within 14 days of baseline assessment):

- Demographic data including height and weight.
- Medical history including details of stress urinary incontinence, previous bladder/kidney infections and any current/previous urological treatments.
- Physical examination including a detailed urological history to assess urinary symptoms and symptoms of bowel function, sexual function and pelvic organ prolapse.
- Details of all medication (over-the-counter and prescription) and dietary/herbal supplements in the previous 6 months.
- Urine pregnancy test to confirm subject is not pregnant (women of child-bearing potential only).
- Complete the Medical, Epidemiologic and Social Aspects of Aging Urinary Incontinence (MESA) Questionnaire (patient quality of life questionnaire).
- Complete a standardized stress test to evaluate amount of urine lost following a standardized bladder-filling protocol verified by ultrasound bladder scanning (provocative pad weight

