11.5 Maintenance of Randomisation and Blinding

A randomisation schedule will be provided. The randomisation schedule is in a permuted block-format randomisation, stratified by study site, to ensure that the subject allocation at the sites remains balanced.

The Subject ID number, randomisation date and patient initials will be recorded along with the allocated treatment.

It is not anticipated that there will be any need to unblind (break the randomisation code) of any subject participating in the study because of an adverse event/adverse device effect, however, the information will be available at the site via the unblinded personnel.

One member of the investigational site team will be responsible for patient training and will consequently be unblinded to required treatment instructions for training. A different member of the team will be responsible for all other patient assessments and CRF completion.

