14.3 Appendix III. Stress Test Protocol

Where possible the assessment will be performed by the same examiner each time for the duration of the study, for a given subject, as follows:

Balance Calibration

- All pad weights will be weighed using a balance supplied by the Sponsor.
- On each day of the assessments and prior to the weighing of the pads, the balance will be calibrated using calibration weight supplied by the Sponsor and the details recorded to verify the balance is operational.
- All zip-lock freezer bags will be weighed in a container to minimise any weight fluctuations.

Bladder Filling Protocol

- Prior to the stress 1h pad test, a pad (moderate POISE) is placed in a zip-lock bag (Weight A).
- Subjects are advised to attend the clinic with a comfortably full bladder.
- Following the pregnancy test, the subject voids the bladder and then drinks 500 mL of water.
- The subject is instructed not to go to the toilet and waits for 1 hour.
- After approximately 1 hour, the Investigator will check that natural diuresis has resulted in a bladder volume of more than 250mL as confirmed by ultrasound or other appropriate method.
- If the bladder volume is not 250mL or more, the subject will be instructed to wait for approximately 30 minutes when it will be re-checked. The exact bladder volume will be recorded.
- On confirmation the bladder volume is 250mL or more, the pad is handed to the subject in the bag and the subject is instructed to attach the pad in their underwear and put the packaging and pad liner back in the zip-lock freezer bag.

Stress Test Protocol is a modified version of the provocative test determined by Bo, 1999.

- The metronome is set to 132bpm.
- The subject is instructed not to contract their pelvic floor muscles but to ‘leak’ as usual.
- The subject is then instructed to run on the spot (with their knees bent) for 30 seconds followed immediately by 30 seconds of jumping jacks (with their arms straight and legs as wide as they can).
- The subject will be encouraged to keep pace with the metronome during the test. If the subject cannot, it will be documented how much of the protocol was completed to establish their baseline. This exact test must then be used in subsequent follow up visits.
- The subject will be asked to sit and stand 10 times from a chair, (the same chair to be used in repeated tests)
- The subject will cough forcefully 10 times
- The subject will pick an object, e.g a pencil, off the floor 5 times.

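### Section 7.3 gives the blinded Investigator, who also recruits, the device log and responsibility for stock, leaving open a route to predicting the next allocation

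*Protocol*

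**What the plan says.** **Log and stock.** Protocol section 7.3: "The Investigator will be provided with a Device Accountability Log to track disposition of all devices including the itouch Sure Pelvic Floor Exerciser". The same section makes the Investigator responsible for correct storage and for returning the devices. It does not mention unblinded staff.

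**Blinding.** Section 7 (opening paragraph): "The investigator and those administering the 1-hour provocative stress test, evaluating adverse events and reviewing diary data are to remain blinded". Under section 7.8 (if necessary) and section 8.8 (in an emergency), the investigator may be told the allocation by the unblinded personnel at the site.

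**Recruitment and baseline.** Under section 8.5, women attending the clinic "will be approached by the Investigator to take part in the clinical study", and section 8.3 gives the consent discussion to the Investigator. Section 8.10 assigns the baseline assessments to designated blinded personnel, but in Appendix III "the Investigator will check that natural diuresis has resulted in a bladder volume of more than 250mL" before the stress test starts.

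**Allocation.** Section 11.5 specifies "permuted block-format randomisation, stratified by study site". The ratio is 1:1 (section 7.5). No block size is given. On the envelopes, section 8.8 says: "Access to these randomisation envelopes will be limited to the designated un-blinded personnel working on the study at the site". It also requires all baseline assessments to be finished before randomisation.

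**Boxes.** Under section 7.2.1 the Vital Compact comes "in a box with an identifying serial number, part number and subject number"; the itouch Sure box carries a serial number and a subject number. Under section 8.7 an eligible woman takes the next available subject number.

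**The concern.** The plan protects concealment by controlling the envelopes. The next allocation can also be inferred from what has already been dispensed, and section 7.3 places that record, for both devices, with the role that approaches and consents the women. Within small site-level blocks, past assignments carry information about the next one.

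Someone who can anticipate the next device can influence who is entered and when, even without intending to. Such selection is hard to detect afterwards, and an intention-to-treat analysis does not remove it. The trial is pivotal, subjects know their device, and the non-inferiority margin is only 5 points, so a modest shift in case mix would matter. Apart from prediction, holding a log of both devices is at odds with the rule that the investigator stays blinded.

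**Working it through.** **1. The passages side by side.**
- Section 7: the investigator is blinded.
- Sections 7.8 and 8.8: the investigator learns an allocation through unblinded personnel, when needed.
- Section 7.3: the Investigator receives the log for both devices and answers for storage.

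Taken literally, 7.3 supplies what the other sections withhold. This conflict does not depend on block size.

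**2. The plan's own figure.** This point rests on no figure in the plan. For reference, the stated 87 per group reproduces: 2 × 0.615 × 0.385 × (1.960 + 1.282)² / 0.24² = 86.4, rounded up to 87. It is unaffected.

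**3. How predictable is the next assignment?** From the documents: about 180 women at about 12 sites, so 180/12 = 15 per site; 1:1; permuted blocks within site. Assumed: the log shows the device for each earlier woman, and the block size 2b is fixed and known (2, 4 or 6).

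Per complete block:
- Share of assignments certain = 1/(b+1): 1/2, 1/3, 1/4.
- Share guessed correctly, always choosing the arm that is behind = [b + (4^b/C(2b,b) − 1)/2]/(2b): 75.0%, 70.8%, 68.3%.

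At 15 women the last block is incomplete, which lowers both shares:

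| Block size | Blocks | Certain | Best guess right |
|---|---|---|---|
| 2 | 7 full + 1 woman | 7/15 = 46.7% | (7 × 1.5 + 0.5)/15 = 73.3% |
| 4 | 3 full + 3 women | (3 × 4/3 + 1/3)/15 = 28.9% | (3 × 2.833 + 1.833)/15 = 68.9% |
| 6 | 2 full + 3 women | (2 × 1.5 + 0)/15 = 20.0% | (2 × 4.1 + 1.7)/15 = 66.0% |

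Chance is 50% right and none certain. A simulation of 40,000 sites agrees to within 0.1 point.

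**4. Would varying the block size be enough?** With sizes 4 and 6 mixed at random and undisclosed, choosing the arm that is behind at the site is still right about 68% of the time (simulated, 15 women). With 4, 6 and 8 it is about 66%. So this alone does not close the route.

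**5. What selection would be needed to matter?** Let g be the share guessed correctly. Let s be the difference in expected response rate between women entered when one device is expected and those entered when the other is. The bias in the responder difference is g·s − (1 − g)·s = (2g − 1)·s. A bias equal to the 5-point margin then needs s = 5/(2g − 1):
- block size 2: 5/0.467 = 10.7 points
- block size 4: 5/0.378 = 13.2 points
- block size 6: 5/0.320 = 15.6 points

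Nothing in the documents estimates s. These are benchmarks, not predictions.

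**6. Boxes.** Section 7.2.1 has boxes provided with a subject number, and section 8.7 issues numbers in order. If numbers are applied before allocation and the boxes can be told apart by device, the next box shows the next allocation. If they are applied after the envelope is opened, it shows nothing. The text does not say which.

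**The case against.** The plan shows clearly where allocation knowledge should sit. The synopsis and section 2.5 place the staff who allocate devices in the unblinded group. Section 11.5 separates the unblinded trainer from the person doing all other assessments. Monitors check that blinding holds. Section 7.3 can be read as ordinary responsibility wording: section 11.2.1 likewise makes the Investigator responsible for completing every eCRF, while 11.5 gives CRF completion to a team member. The log form is not shown, and 7.3 speaks only of disposition. The box label is a template with one text covering both devices, and envelopes would have little purpose if boxes were already numbered. Block sizes may already vary and be withheld from sites.

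Much of this stands, and it rules out a stronger reading. A reader might infer that the Investigator runs the baseline eligibility test and can work out the next allocation, or see it on the shelf. The documents do not support that:
- Section 8.10 gives the baseline assessments to blinded personnel. The Investigator's written part is the bladder-volume check, and the exact volume is recorded.
- Section 7.3 assigns responsibility, not necessarily physical custody.
- A subject-level log and pre-numbered boxes are inferences.
- Certainty covers only part of each block, and only if the block size is known.

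What the objection does not supply is any sentence that moves the log or the stock to unblinded staff, or that says when boxes are numbered.

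**Conclusion.** The point holds as an unclosed route, not as a demonstrated failure of concealment. Section 7.3 as written conflicts with section 7 and with sections 7.8 and 8.8, and the envelope restriction does not resolve that. If the log is subject-level and blocks of 2, 4 or 6 are known or inferred, 47%, 29% or 20% of assignments are certain at 15 women per site, and 73%, 69% or 66% can be guessed. The exposure through the boxes is conditional on numbering before allocation.

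The size of any bias is unknown. A reader might go on to quote an inflated false non-inferiority rate. For example, a 3.3-point shift at true rates of 47% and 52% with 90 per arm (SE 7.44 points) gives 1 − Φ(1.96 − 3.3/7.44), about 6.5% instead of 2.5%. The arithmetic is right, but no document supports a shift of that size, or that anyone would act on foreknowledge. The case for change is that the contradiction is in the text, selection cannot be repaired in analysis, and closing the route is nearly free.

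**What to change.** - **Section 7.3:** assign device stock and the subject-level accountability log to the designated unblinded personnel only. The Investigator keeps oversight but does not see the subject-level log until database lock.
- **Section 7.2.1:** state that the unblinded person puts the subject number on the box only after the envelope is opened.
- **Section 11.5 (optional):** use varying block sizes withheld from sites. This is not sufficient alone.

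An eCRF lock on eligibility before the envelope is opened would mostly repeat the rule in section 8.8 that baseline is completed before randomisation.

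The cost is protocol wording, a handwritten number at dispensing, and later Investigator sign-off of the log. The unblinded staff and envelopes are already in the plan, and no extra women or visits are needed.
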